PROMISER Registry

Version 3, March 9, 2026

“PROspective study of MInimally invaSIve abdominal wall hERNia repair”

Protocol Code: PROMISER2026

[REDACTED NAME]

General and Digestive Surgery. Fundación Jiménez Díaz

CONTENTS

- 1 Summary
- 2 Introduction and Study Justification
- 3 Hypothesis and Study Objectives
- 4 Study Type and Design
- 5 Subject Selection
- 6 Study Development and Evaluation of Results
- 7 Adverse Event Management
- 8 Ethical Aspects
- 9 Practical Considerations
- 10 Statistical Analysis
- 11 Study Publication
- 12 Bibliography

SUMMARY

Study Identification

Title:

Prospective study of minimally invasive abdominal wall hernia repair

Code: PROMISER

Version: January 1, 2026

Sponsor:

Research Institute of Fundación Jiménez Díaz, Madrid.

Research Team Responsible:

Principal Investigators:

- [REDACTED NAME]
- [REDACTED NAME]

Co-investigators:

- [REDACTED NAME]
- [REDACTED NAME]
- [REDACTED NAME]
- [REDACTED NAME]

Study Centers:

Hospital Universitario Fundación Jiménez Díaz

Ethics Committee:

CEIm of Hospital Universitario Fundación Jiménez Díaz

OBJECTIVES

Primary Objective:

To investigate the recurrence rate of hernias repaired using these techniques.

Secondary Objectives:

- Determine surgical complications and associated morbidity and mortality
- Assess pain and quality of life
- Investigate reoperation rates
- Describe risk factors for hernia formation
- Define the usefulness of prehabilitation programs

STUDY DESIGN

Prospective observational dynamic cohort.

DISEASE UNDER STUDY

Primary and incisional ventral hernias.

POPULATION

Approximately 80 patients per year.

TIMELINE

Start: March 2026

Total duration: 10 years

INTRODUCTION AND JUSTIFICATION

Ventral and incisional hernias are among the most frequent conditions in general surgery and represent a major public health problem due to their high prevalence, recurrence rates, and impact on quality of life.

Minimally invasive techniques (laparoscopic and robotic) have significantly changed surgical management, showing advantages such as fewer complications, less pain, and shorter hospital stays.

However, they also have limitations, including higher costs, longer operative times, and a significant learning curve.

This study aims to evaluate recurrence, pain, quality of life, complications, and long-term outcomes.

HYPOTHESIS

This is a descriptive study aiming to estimate 5-year recurrence with $\pm 4\%$ precision.

PRIMARY OBJECTIVE

Evaluate recurrence rate after minimally invasive abdominal wall surgery.

SECONDARY OBJECTIVES

- Surgical complications and morbidity/mortality
- Pain and quality of life
- Reoperation rates
- Risk factors
- Role of prehabilitation

STUDY DESIGN

Prospective observational cohort.

SUBJECT SELECTION

Adult patients undergoing minimally invasive surgery.

INCLUSION CRITERIA

Patients indicated for minimally invasive abdominal hernia repair.

EXCLUSION CRITERIA

- Age <18
- Refusal to participate
- Only inguinal hernias
- Not candidates for minimally invasive surgery

SAMPLE SIZE

Approximately 400 patients over 5 years.

STUDY DEVELOPMENT

Includes preoperative, 3-month, 12-month, and long-term follow-up visits.

VARIABLES

Demographics, clinical history, surgical details, complications, and outcomes.

RESULT EVALUATION

Primary analysis includes recurrence rate and Kaplan-Meier curves.

Secondary analysis includes complications, pain, quality of life, and reintervention.

LIMITATIONS

No external control group.

ADVERSE EVENTS

Observational study with no additional interventions.

ETHICS

Conducted according to the Declaration of Helsinki and data protection laws.

CONFIDENTIALITY

All personal data anonymized and coded.

INSURANCE

No insurance required due to observational nature.

ECONOMIC REPORT

No funding or compensation.

PRACTICAL CONSIDERATIONS

Data recorded according to Good Clinical Practice.

STATISTICAL ANALYSIS

Descriptive and analytical statistics, including regression and survival analysis.

PUBLICATION

Results will be published in scientific journals.

BIBLIOGRAPHY

(References maintained as in original document)

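### The primary 5-year recurrence figure is tied to Kaplan-Meier with no competing-risk estimator; if deaths are censored, it modestly overstates the actual recurrence risk

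*Protocol*

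**What the plan says.** The protocol describes the primary analysis in one sentence, under Result Evaluation: "Primary analysis includes recurrence rate and Kaplan-Meier curves". The Statistical Analysis section adds only "Descriptive and analytical statistics, including regression and survival analysis". Neither section names a competing-risk estimator or rules one out, and neither says whether a death is censored, counted as an event or treated in some other way.

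The target is set under Hypothesis: "This is a descriptive study aiming to estimate 5-year recurrence with" a precision of ±4%. The Exclusion Criteria remove patients under 18 but set no upper age limit. The secondary objectives in the Summary include "Determine surgical complications and associated morbidity and mortality". No expected recurrence rate and no expected death rate is given anywhere.

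**The concern.** A patient who dies without a recurrence can no longer have one. A Kaplan-Meier analysis that censors the death treats that patient as still at risk and as represented by those who remain under observation. One minus Kaplan-Meier then answers a hypothetical question: what proportion would recur by 5 years if no one died first? It is never below the cumulative incidence, which is the proportion who do recur, and it lies above it once a death without recurrence is followed by a recurrence in someone else. Counting deaths as events gives recurrence or death combined, which is a different quantity again.

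The study calls itself descriptive and wants a 5-year recurrence figure. Most readers will take that figure as the share of repaired patients whose hernia came back. In adults with no upper age limit some deaths within 5 years are foreseeable, so the published number could be somewhat higher than the quantity readers think they are given. This is a systematic difference, so its confidence interval does not allow for it.

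**Working it through.** **Step 1: the plan's own figures.** The Summary gives "Approximately 80 patients per year" and the Sample Size section gives "Approximately 400 patients over 5 years". 80 × 5 = 400, so these agree. For precision, assume a 95% interval (the level is not stated) and a simple proportion with complete follow-up. The half-width is 1.96 × √(p(1 − p)/400).

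- At p = 0.20 it is 1.96 × √(0.16/400) = 1.96 × 0.02 = 0.0392, or 3.9 points.
- It equals 4.0 points at p of about 21.1%.

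Since no p is given, the precision target neither confirms nor refutes 400. The calculation does make 20% a convenient illustrative value for what follows.

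**Step 2: inputs.** The 5-year horizon and the ±4 points come from the Hypothesis section. Kaplan-Meier recurrence at 5 years (R) and 5-year mortality (D) are my assumptions. So are constant, independent hazards for recurrence and death.

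**Step 3: formulas.**

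- λ = −ln(1 − R)/5 and μ = −ln(1 − D)/5
- One minus Kaplan-Meier at 5 years, deaths censored: 1 − exp(−5λ) = R
- Cumulative incidence at 5 years: λ/(λ + μ) × [1 − exp(−5(λ + μ))]

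**Step 4: worked example, R = 20%, D = 10%.**

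- 5λ = −ln 0.8 = 0.2231 and 5μ = −ln 0.9 = 0.1054.
- λ/(λ + μ) = 0.2231/0.3285 = 0.679.
- 1 − 0.8 × 0.9 = 0.28.
- Cumulative incidence = 0.679 × 0.28 = 0.190, against 0.200 from Kaplan-Meier.

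**Step 5: overstatement at 5 years, in percentage points.**

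| Kaplan-Meier value | D = 5% | D = 10% | D = 20% |
|---|---|---|---|
| 10% | 0.25 | 0.5 | 1.0 |
| 20% | 0.5 | 1.0 | 2.0 |
| 30% | 0.7 | 1.4 | 2.9 |

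As a hand check, the gap is close to R × D/2; for example 20% × 10%/2 = 1.0 point.

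**Step 6: comparison with the precision target.** Under the same model, the gap reaches 4 points only at 5-year mortality of about 68%, 38% or 27%, for Kaplan-Meier values of 10%, 20% or 30%. A smaller gap still has an effect. If ±4 points is a 95% half-width, the standard error is 4/1.96 = 2.04 points. As an interval for the actual cumulative incidence, its coverage falls from 95% to about 92% with a shift of 1.0 point (1.0/2.04 = 0.49 standard errors), and to about 83% with a shift of 2.0 points (0.98 standard errors).

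**The case against.** The strongest reply is that the protocol commits to less than the concern assumes. The primary analysis is said to include Kaplan-Meier, which is not exclusive, and a recurrence rate is listed beside it. No censoring rule is stated, and such rules are commonly left to a statistical analysis plan, which is not at hand. Censoring deaths is also legitimate if the aim is the durability of the repair in the absence of death, and the word descriptive does not settle which quantity is meant. All of this stands, so the point is conditional and the silence on censoring is not itself a fault. What remains is that the only time-to-event estimator named for the primary outcome does not, in its usual form, give the descriptive quantity that the aim most naturally suggests.

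A reader might infer several stronger points that the document does not support:

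- **Kaplan-Meier is fixed as the sole method.** The wording leaves room for other estimators.
- **Patients are followed for 5 to 10 years, so the error is much larger.** With the hazards of the worked example, a 10-year Kaplan-Meier value of 36.0% would compare with 32.7%. But "Total duration: 10 years" is the length of the study and not a 10-year endpoint. After 12 months the visits are described only as long-term, and a "Prospective observational dynamic cohort" implies varying follow-up.
- **Risk-factor comparisons are distorted.** Cause-specific hazard regression, which censors deaths, is a standard approach to that question, and the protocol lists regression without saying that risk factors will be compared by Kaplan-Meier.
- **The change costs nothing because mortality is already collected.** The mortality objective is worded around surgical complications and does not clearly secure dates of late deaths from any cause.

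**Conclusion.** The concern holds in a limited form. If deaths are censored and the figure is read as actual risk, the 5-year recurrence estimate is too high by about 0.5 to 2.0 points, for a Kaplan-Meier value of 20% and 5-year mortality of 5% to 20%. The result rests on assumed rates, on constant independent hazards, and on conventional censoring that the protocol does not state. The gap stays below the ±4-point target unless mortality is high, so the primary result is not invalidated. It is nevertheless systematic, a larger sample would not remove it, and a standard estimator avoids it. This is a worthwhile and inexpensive improvement, not a condition for the study to proceed.

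**What to change.** In Result Evaluation, name the target and the estimator. Suggested text:

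> Five-year recurrence will be estimated as the Aalen-Johansen cumulative incidence at 60 months, with death from any cause as a competing event and a 95% confidence interval. Kaplan-Meier curves with deaths censored will be shown as supporting information. Reoperation will be analysed in the same way.

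If the investigators instead want recurrence in the absence of death, they should say so and still report the cumulative incidence alongside.

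The costs are modest. The estimator is in standard software and needs no additional patients. The date of death from any cause must be recorded throughout follow-up, which the present mortality objective does not clearly provide for. The headline recurrence figure may be slightly lower than a Kaplan-Meier figure, which should be kept in mind when it is set beside published Kaplan-Meier results; the supporting curve serves that comparison.
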